6.1 Reference Sampling Model

In a general sense, the aerosol application study involves selecting N_C buildings and then conducting N_M MEs within each building. This results in a total of $N=N_C\times N_M$ monitoring events. The simplest reference model would be one that treats the N MEs as a simple random

sample of N independent applicator-days from a population of future applicator-days. However, if there is a correlation between MEs conducted in the same building, the sample sizes calculated from this reference model will be too small. A better reference model would accommodate this simple type of ME correlation. More complicated reference models that incorporate specific aspects of the sampling and random assignments could also be proposed. However, such models would be of little practical value since they would require estimates for many parameters for which no information is available.

For the aerosol application study, therefore, random nested sampling will be used as a reasonable reference model for the combination of random sampling, randomization, and diversity selection actually used. This reference model assumes that:

- 1. Exposure, normalized by the amount of active ingredient handled, is lognormally distributed with a known geometric standard deviation (GSD). Equivalently, the logarithm of normalized exposure is normally distributed with known standard deviation Log GSD.
- 2. There are N_C clusters (i.e., sites) and N_M MEs per cluster. The total number of MEs is, therefore, $N=N_C\times N_M$.
- 3. There is a possible within-cluster (i.e., within-site) correlation of log normalized exposure. This is referred to as the intra-cluster correlation, or just the ICC.

6.2Benchmark Objective

Benchmark objectives specify accuracy goals that must be achieved within the framework of the reference sampling model when sample size is adequate. In this study, 'sample size' means both the number of clusters (N_C) and the number of MEs per cluster (N_M).

For the aerosol application study, the benchmark objective is that (when the reference model is true) sample estimates of the arithmetic mean and 95th percentile of normalized exposure are accurate to within 3-fold 95% of the time. The EPA, in discussion with AEATF II, determined that this benchmark is sufficient for regulatory purposes.

6.3Expected Variation in Normalized Exposure

Some idea of the variability of normalized exposure is necessary in order to determine the sample size that meets the benchmark objective. In terms of the reference nested-random sampling model, the variation structure is determined by the geometric standard deviation (GSD) and the intra-cluster correlation (ICC). GSD measures the total relative variation between future applicator-days of normalized exposure. The ICC describes how similar within-site exposures are with respect to the total variation in (normalized exposure). An ICC of zero means that MEs within the same cluster are no more similar than are MEs in different clusters. At the other extreme, ICC=1 means that all MEs in the same cluster have identical exposure.

As noted previously, the CMA study (Popendorf et al. 1992) provides the only directly relevant existing data for the aerosol application of antimicrobial pesticides. This study, however, provides just five aerosol applicator monitoring events spread over three different facilities. Although only hand exposures were detectable, these data can provide a crude estimate of total relative variation (GSD). However, the numbers of facilities and MEs per facility are too small to provide a useful estimate of ICC.

Although obtained for crack and crevice insecticide applications, PHED study 521 can provide normalized dermal exposure data for 15 hand-held aerosol monitoring events collected from 15 different residential houses. For this measure, there were no significant differences among the five subjects (p=0.1833). Thus, it is reasonable to treat these as 15 independent MEs for the purpose of estimating total relative variation. As was the case for the CMA study, these data can provide no estimate of ICC since each ME was conducted in a different house.

In addition to the two aerosol studies discussed above, exposure data from additional, non-aerosol application sources are also available (Table 4): The CMA study provided data for mopping applications (6 MEs) and for wiping applications (6 MEs). As is the case for aerosol, both mopping and wiping application are repetitive-motion tasks. Although the magnitude of the normalized exposures for mopping, wiping, and aerosol application are not expected to be the same, the relative variation for repetitive-motion activities might be expected to be driven primarily by variation in subject behavior. If so, then these four sets of data might have a common geometric standard deviation and a more robust estimate of GSD can be obtained by using all of this information.

The feasibility of using the normalized dermal exposure results from the two aerosol data sets or from all four 'repetitive task' data sets together to estimate relative total variation for the aerosol study was first evaluated. Only dermal exposure was considered given that it was associated with higher exposures, i.e., was found to be the primary route of exposure in these studies. Levene's test for equal variability among groups (Glazer, 1983) was applied to the \log_e -transformed, normalized dermal exposure values. These results are summarized in Table 5. Although the \log_e -scale standard deviations (SD) ranged from 0.62 to 1.61 there was no significant difference (p > 0.05) in relative variability among the four data sets. A commonvariance ANOVA model gave a pooled \log_e -scale SD of 0.74 for the two aerosol studies and 1.05 for all four repetitive-motion studies. The corresponding estimates of geometric standard deviation (GSD = exp SD) would then be 2.1 and 2.9, respectively. These two GSD values are considered in the determination of sample size in the next section.

None of these studies can provide an indication of the expected magnitude of the within-cluster correlation (ICC) in normalized exposure resulting from aerosol application. Much of the variation resulting from such a repetitive task is expected to track the variation in worker behaviors and within-facility diversity. In contrast, small variation in indoor environmental conditions (surface types and configurations, temperature, humidity, air exchange rate) is expected across indoor locations (e.g., building types) in which the monitoring events take place. This would suggest an intra-cluster correlation (ICC) near zero. A central tendency ICC value across many outdoor agricultural exposure scenarios, where moderate levels of within-site

correlation are expected, is 0.3 (AHETF, 2007, Appendix C). This represents a likely upper-bound for most indoor antimicrobial exposure scenarios.

Source (Study)-Specific Normalized Dermal Exposure Values for each Monitoring Table 4: Event

		Normalized Dermal	
Source (Study)	Monitoring	Exposure (µg / lbs ai	
	Event ID	handled)	
	47	126,263	
	79	48,913	
CMA (Aerosol, Hands) ^I	80	666,667	
	87	413,043	
	90	340,909	
	521-A-1	2,180,000	
	521-A-2	657,000	
	521-A-3	365,000	
	521-B-4	488,000	
	521-B-5	459,000	
	521-B-6	199,000	
	521-C-7	815,000	
PHED (Aerosol, Study 521) ²	521-C-8	1,140,000	
	521-C-9	1,720,000	
	521-D-10	1,020,000	
	521-D-11	521,000	
	521-D-12	384,000	
	521-E-13	683,000	
	521-E-14	617,000	
	521-E-15	410,000	
	1	20,855	
	5	22,186	
CMA (Mop) ³	7	503,250	
CIVIA (IVIOP)	9	16,656	
	10	34,394	
	11	37,088	
	2	4,313,916	
	6	1,747,115	
CMA (Wipe) ⁴	8	1,058,688	
(··- r -)	61	49,252	
	62	471,758	
	73	2,570,922	

¹ Monitoring events corresponded to separate individuals each treating a different room. Rooms were spread over multiple buildings. Dermal residues were only detectable on hands. Three monitoring events that yielded non-detectable residues for all body parts were excluded.

² Monitoring events corresponded to three separate evaluations of 5 different individuals. Each of the 15 monitoring events occurred in a different house.

Monitoring events corresponded to separate individuals treating a different room (over a variety)

of locations).

Table 5: Estimates of the Variation in Total Normalized Dermal Exposure from Existing Studies.

Study	N	Standard Deviation of Log _e Normalized Exposure
PHED (Aerosol, Study 521)	15	0.62
CMA (Aerosol-Hands)	5	1.05
CMA (Wipe)	6	1.61
CMA (Mop)	6	1.26

Common Relative Variation Models:¹

PHED and CMA Aerosol Studies only:

Common SD of Log _e Exposure	0.74
Common GSD of Exposure ²	2.1

All 4 Repetitive Task Studies:

Common SD of Log _e Exposure	1.05
Common GSD of Exposure ²	2.9

Assuming a separate mean for each study, but a common standard deviation on the log scale.

6.4Determination of Sample Size

A Monte Carlo simulation approach was used to examine the impact of number of clusters (N_C) and number of MEs per cluster (N_M) on accuracy of the arithmetic mean and 95th percentile for the reference model. For each examination 10,000 random data sets were generated using the reference nested-random sampling model and assumed values of the total GSD and the intracluster correlation (ICC). From each simulated set, estimates of the arithmetic mean and 95th percentile were calculated.

The fold relative accuracies (fRA) for the mean and 95th percentile were also computed. If θ is the parameter of interest and T is the corresponding calculated statistic, then fold relative accuracy is defined as:

(1)
$$fRA = \text{Maximum of } T/\theta \text{ and } \theta/T$$

⁴ Monitoring events corresponded to individuals treating a different room. Rooms were spread over multiple buildings. Two monitoring events that yielded non-detectable residues for all body parts were excluded.

²Geometric standard deviation = exp(SD).

Fold relative accuracy simply expresses how far T is from θ in a relative sense. The result is 10,000 random values of fRA. The empirical 95th percentile of these 10,000 fRA values, fRA_{95} , is the quantity of interest. By definition, T is within (fRA_{95}) -fold of θ , 95% of the time. Thus, if 3-fold accuracy is desired, fRA_{95} should be approximately equal to 3. (Note that for historical reasons, the EPA and others sometimes refer to fRA_{95} as the 'K-factor'.) The simulation procedures and the definition of fold relative accuracy are the same as those used for the AHETF monitoring program (AHETF, 2007, Appendix C). This simulation method and its theoretical basis are described in greater detail in the AHETF documentation.

For a configuration of N_C =3 clusters (i.e., sites or buildings), Table 6 shows the sample size necessary to achieve 3-fold relative accuracy with GSD=2.1 or GSD=2.9 and an intra-cluster correlations (ICC) as high as 0.3. For the aerosol-only GSD of 2.1, only 2 MEs per cluster are needed giving a total of N=6 MEs for the aerosol scenario. However, when the more robust repetitive-motion task GSD of 2.9 is used, 6 MEs per cluster are required giving N=18 MEs for the scenario. Given the sensitivity of the sample size to GSD and the belief that the repetitive-motion GSD is a better indicator of the expected true relative variation for this scenario, the AEATF II prefers to assume GSD=2.9 for the purposes of determining sample size. As also shown in Table 6, smaller, and perhaps more likely, ICCs will yield accuracies much better than 3-fold.

Table 6: Relative accuracy profile when there are N_C =3 clusters (sites) and the number of monitoring events per cluster (N_M) is chosen to give 3-fold accuracy or better at ICC=0.3.

	95% Bound on Relative Accuracy (fRA ₉₅) or "K-factor"				
ICC	Aerosol Studies GSD of 2.1 N _M =2 MEs per cluster		Repetitive Task St N _M =6 MEs		
	Arithmetic Mean	95th Percentile	Arithmetic Mean	95th Percentile	
0	2.0	2.6	1.9	2.2	
0.1	2.0	2.7	2.1	2.4	
0.2	2.1	2.8	2.3	2.7	
0.3	2.1	3.0	2.5	3.0	

It is also possible to obtain equivalent accuracies with different configurations of N_C and N_M . For example, when GSD=2.9 the three configurations listed in Table 7 are essentially equivalent. Although they may be statistically equivalent, the configuration with fewer clusters and more MEs per cluster (and more total MEs) is actually more cost effective and also permits a greater diversity in amount of product applied within each cluster. Thus, a design of 3 sites and 6 MEs per site appears reasonable if the reference model is assumed. By analogy, this configuration

will be used for the aerosol application study as well.

Table 7: Practically equivalent configurations of clusters and MEs per cluster when ICC=0.3.

Number of Clusters, N_C	-	fRA ₉₅ for 95 th Percentile		
	MEs per Cluster, N _M	MEs per Cluster, N _M Total MEs, N	ICC=0	ICC=0.3
3	6	18	2.2	3.0
4	4	16	2.2	2.8
6	2	12	2.6	2.8

6.5Building/Room Categories and Product Use Intervals

The scenario design in Section 6.4 indicated that NC=3 clusters are required. As discussed in Section 5.2 each of these three clusters of MEs should be conducted at a monitoring site that can be generally described as a qualifying commercial lodging facility (i.e., hotel, motel with kitchenette or full kitchen). MEs will be conducted in available bathrooms and, if present, food preparation areas within the facility. A food preparation area (or FPA) is defined as a room containing a stove/oven, refrigerator, and food preparation sink.

A simple random sample of qualifying facilities could be selected. However, this might result in two or more monitoring sites with similar configurations of ME-appropriate rooms. Although valid, greater diversity among monitoring sites can be obtained if each of the three clusters is conducted in a somewhat different room configuration. Consequently, for the aerosol application study the AEATF II will consider only the following three building/room configuration categories:

- A. Hotels/motels with 20 or more available units containing full kitchens
- B. Hotels/motels with 20 or more available units containing kitchenettes
- C. Hotels/motels with 20 or more bathroom-only units.

These three categories were chosen because they vary with respect to bathroom and FPA (i.e., kitchen or 'kitchenette') configurations which might be expected to impact exposure potential differently. Although other, equally acceptable, classifications could be proposed, this one is considered both intuitive and logistically practical.

As described in Section 5.2 above, one facility will be randomly selected from each category. It is important to emphasize that this study is not concerned with testing whether average exposure differences exist between the three different configuration categories. Nor would it be especially relevant if true exposure differences actually do not exist, on the average, between these categories. Rather, the purpose of the patterned randomization is simply to reduce the likelihood that the three selected monitoring sites will be too similar by chance.

The scenario design also requires $N_M=6$ MEs within each cluster. As noted in Section 5.3, each of these MEs will require an amount of product in the range of 1 to 4 19oz cans. Thus, a reasonable approach is to require that the six MEs have applicators apply product amounts somewhere within the following six ranges:

A. 1 to 1.5 cans

B. 1.5 to 2 cans

C. 2 to 2.5 cans

D. 2.5 to 3 cans

E. 3 to 3.5 cans

F. 3.5 to 4 cans

Ranges for the different product application volumes are used since partial can amounts are difficult to control exactly without impacting the behavior of an applicator. Actual product levels are not randomly assigned within each interval. Rather, each applicator will be asked to stop applying when the ME observer estimates that the amount applied is somewhere in the target interval assigned to the ME.

The N=18 randomly sampled professional applicators will be randomly assigned to the N=18 combinations of building/room configuration category and application volume illustrated in Table 8. This provides a diverse set of MEs with respect to three meta-parameters: (1) applicator, (2) types of rooms, and (3) product volume applied.

Table 8:	The structure	of the $N=1$	8 MEs proposec	I for the aeroso	l application study

Number of 19 oz	Building/room configuration category				
cans applied per ME	Motel with bathrooms and Full Kitchen FPAs	Hotel/motel units with bathrooms and Kitchenette FPAs	Hotel/motel units with bathrooms only		
1 to 1.5	•	•	•		
1.5 to 2	•	•	•		
2 to 2.5	•	•	•		
2.5 to 3	•	•	•		
3 to 3.5	•	•	•		
3.5 to 4	•	•	•		

It is reasonable to ask if it would be simpler to abandon the attempt to structure diversity in building/room configuration and application volume. One might simply select three facilities at random from among the qualifying facilities in Fresno County. In addition, six application volumes anywhere between 1 and 4 cans could also be randomly selected. Table 9 illustrates possible consequences of such an unstructured approach. Because facility selection was completely at random, one category was missed and two monitoring sites in another category (motel with full kitchen) were selected by chance. This still provides some diversity, but not as much as provided by the stronger diversity selection approach in Table 8. The randomly selected application volumes cover all but the 1 to 1.5 can amounts. But there is no balance within each facility and some of the intervals are more heavily represented than others.

Number of 10	Building/room configuration category				
Number of 19 oz cans applied per ME	Motel with and full		Hotel/motel units with bathrooms and kitchenette FPAs	Hotel/motel units with bathrooms only	
1 to 1.5					
1.5 to 2	•••	•			
2 to 2.5		•••		••••	
2.5 to 3				••	
3 to 3.5	•	••			

Table 9: A structure of the N=18 MEs generated by randomly selecting building and product amount

Table 9 illustrates only one example of the possible random configurations that could be generated. However, the lack of diversity shown by this configuration is rather typical of other randomly generated configurations. In general, when sample sizes are relatively small, random selection is less likely to produce a diverse set of MEs. Although neither of the approaches shown in Tables 8 and 9 can yield a true random sample of future applicator days, it is felt that the diversity selection approach (Table 8) will be better able to characterize the future applicator-day diversity in exposure. On balance, therefore, the AEATF II considers that constructing MEs with the greater diversity shown in Table 8 is well worth the additional effort.

It should be noted that the ME design illustrated in Table 8 has the superficial appearance of a fixed-effect treatment structure with two fixed factors: building/room configuration category and application volume. In such an experimental framework this could be thought of as 18 experimental units (applicators) assigned to 18 design points (combinations of category and amount). However, regulatory agencies and most other users of these data will prefer to view these MEs not as a fixed-factor 'comparative' experiment, but merely as a set of N=18 synthetic applicator-days that characterize the diversity of exposures possible for the aerosol application scenario. This 'diversity characterization' objective was envisioned by AEATF II when determining sample size. A statistical comparison of exposure between building types or between application volumes was not envisioned as an objective for the purpose of sample size determination. However, statistically sophisticated users of these data are always free to analyze such aspects of the exposure data if they so desire.

7. References

3.5 to 4

AEATF II (Antimicrobial Exposure Assessment Task Force II). 2008. Governing Document for a Multi-Year Antimicrobial Chemical Exposure Monitoring Program. Interim Draft Document. American Chemistry Council, Arlington, VA.

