PHED study 521 meets some of the AEATF II acceptance criteria for evaluating existing data. Although acknowledging that these data are of limited value, the EPA does use this study for antimicrobial exposure assessments. However, because the aerosol product was not an antimicrobial product and there was a lack of diversity with respect to amount of AI handled (and an associated range of duration of product spraying), additional data are needed. It is also noteworthy that descriptions of study 521 or 456 provided in PHED do not include particle size distribution documentation.

3.2CMA Study

In addition to PHED, another source of existing data being used by regulatory agencies in the case of antimicrobials is the *Chemical Manufacturers Association Antimicrobial Exposure Assessment Study* directed by [name] at the University of Iowa (Popendorf et al. 1992). In total, the CMA study obtained both dermal and inhalation exposure measurements for 88 separate monitoring events (MEs) using nine different application methods (pour liquid, pump, pour solid, place solid, aerosol spray, high pressure spray, low pressure spray, mop and wipe). For aerosol (pressurized canisters), trigger-sprayed aerosol, and wiping applications, exposures to the active ingredients ortho phenyl phenol (OPP) and ortho benzyl p-chlorophenol (OBPCP) were measured.

In the CMA study aerosol application (for the purpose of disinfecting) resulted in only five MEs with measurable exposures. Only hand exposures were detectable for these MEs. MEs were conducted in different rooms distributed over a dental office, private residences, and public buildings. The applicators were dental office employees, professional housekeeping staff, or members of the general population. All applications were made using products contained in aerosol spray cans. The application duration, only a fraction of which involved actual aerosol spraying, ranged from 9 to 260 minutes.

Based on EPA's review (Mostaghimi 1995), CMA's study data met some regulatory agency requirements, but were lacking in other areas. In particular, the following areas of the CMA study were found to be lacking:

- 1) Good laboratory practice, especially in the area of providing quality assurance, was not always followed closely.

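### The planning GSD of 2.9 leaves out five non-detect monitoring events, so 3-fold accuracy at ICC 0.3 is not demonstrated for 18 MEs

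*Combined protocol and SAP*

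**What the plan says.** Section 6.2 sets the accuracy goal: "sample estimates of the arithmetic mean and 95th percentile of normalized exposure are accurate to within 3-fold 95% of the time". Section 6.3 takes the spread from PHED study 521 (15 MEs) and the CMA aerosol (5), wipe (6) and mop (6) data. It reports that the log-scale "standard deviations (SD) ranged from 0.62 to 1.61", with a pooled "SD of 0.74 for the two aerosol studies and 1.05 for all four repetitive-motion studies".

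The exclusions appear only in the footnotes to Table 4. For CMA aerosol: "Three monitoring events that yielded non-detectable residues for all body parts were excluded". For CMA wipe: "Two monitoring events that yielded non-detectable residues for all body parts were excluded". Section 3.2 says that the CMA aerosol work "resulted in only five MEs with measurable exposures".

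In Section 6.4 the task force "prefers to assume GSD=2.9 for the purposes of determining sample size" and concludes that "6 MEs per cluster are required giving N=18 MEs for the scenario". Table 6 gives fRA95 = 3.0 for the 95th percentile and 2.5 for the arithmetic mean at ICC 0.3, the largest ICC considered.

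**The concern.** A non-detect is a left-censored observation: its value is unknown but lies below a limit. Dropping such observations before computing a log SD discards information about the lower part of the distribution and will usually make the spread look smaller. Here 3 of 8 CMA aerosol MEs and 2 of 8 CMA wipe MEs were dropped, and these sets supply 9 of the 28 degrees of freedom in the pooled SD.

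The pooled SD sets the sample size. The number of MEs per site was chosen so that Table 6 just reaches 3-fold at ICC 0.3, so a modest rise in GSD takes the 95th percentile past the benchmark. Section 5.4 discusses values below the LOQ only as a source of overestimated exposure. The plan nowhere considers their effect on the planning GSD.

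**Working it through.** **Inputs.** Exposure values: Table 4. Exclusions: Table 4 footnotes 1 and 4. Model and benchmark: Sections 6.1, 6.2 and 6.4. The detection limits and amounts handled for the five MEs are not given, so they are assumed and varied.

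**1. Table 5 reproduces.** Sums of squares of log exposure about each study mean:
- PHED 521: 5.460 (14 df)
- CMA aerosol: 4.384 (4 df)
- CMA wipe: 12.881 (5 df)
- CMA mop: 7.974 (5 df)

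Pooled SD = √(30.699/28) = 1.047, GSD = exp(1.047) = 2.85; the rounded SD gives exp(1.05) = 2.86, the plan's 2.9. Aerosol only: √(9.844/18) = 0.740, GSD 2.09.

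**2. Table 6 reproduces.** Nested lognormal model with s = ln GSD, between-site variance ICC·s² and within-site variance (1−ICC)·s², 200,000 data sets, 3 × 6 MEs. The 95th percentile is estimated by exp(m + 1.645·sd). fRA95 was computed in two ways: as Section 6.4 defines it (95th percentile of the larger of T/θ and θ/T), and as the larger of the 2.5% and 97.5% bounds on T/θ. For GSD 2.9:

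| ICC | Plan | Text definition | 2.5/97.5% bounds |
|---|---|---|---|
| 0 | 2.2 | 2.15 | 2.18 |
| 0.1 | 2.4 | 2.33 | 2.41 |
| 0.2 | 2.7 | 2.54 | 2.68 |
| 0.3 | 3.0 | 2.80 | 2.98 |

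The plan's figures match the bounds version. At ICC 0.3, 3-fold is lost once GSD exceeds about 2.9 (bounds) or 3.1 (text definition).

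**3. Simple substitution.** With the five put back there are 33 df.
- At each group's lowest detect (48,913 aerosol; 49,252 wipe): the sums of squares become 5.460 + 8.757 + 25.386 + 7.974 = 47.577. SD = √(47.577/33) = 1.201, GSD 3.32.
- At half the lowest detect: √(59.172/33) = 1.339, GSD 3.82.
- At the group geometric mean: √(30.699/33) = 0.965, GSD 2.62.

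The pooled GSD passes 2.9 when the five are set below about 2.5 times the lowest detect, and 3.1 below about 1.5 times.

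**4. Censored fit in the plan's own model** (separate means, common log SD). A detect contributes the normal density of its log value; a non-detect contributes Φ((ln L − μ)/σ), with L the assumed limit. The df-corrected column multiplies the ML σ by √(32/28), which gives the plan's pooled SD when there is no censoring.

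| Assumed limit | GSD, ML | GSD, df-corrected |
|---|---|---|
| Group's highest detect | 2.62 | 2.80 |
| Group geometric mean | 2.66 | 2.85 |
| 2.5 × lowest detect | 3.05 | 3.30 |
| Lowest detect | 3.59 | 3.92 |
| Half the lowest detect | 4.19 | 4.63 |

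**5. Accuracy of 3 × 6 MEs at these GSDs** (95th percentile; text definition / bounds):

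| GSD | ICC 0 | ICC 0.1 | ICC 0.2 | ICC 0.3 |
|---|---|---|---|---|
| 2.85 | 2.1 / 2.2 | 2.3 / 2.4 | 2.5 / 2.6 | 2.8 / 2.9 |
| 3.32 | 2.4 / 2.4 | 2.6 / 2.7 | 2.9 / 3.0 | 3.2 / 3.4 |
| 3.9 | 2.7 / 2.7 | 3.0 / 3.1 | 3.3 / 3.5 | 3.7 / 4.0 |

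At GSD 3.32 and ICC 0.3 the arithmetic mean has fRA95 of 2.8 by the text definition (about 3.0 for the plain sample mean by the bounds).

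**The case against.** The strongest reply is that the analysed quantity is exposure per pound of active ingredient handled. Sections 4.1 and 5.4 link non-detects to small amounts of product. A small amount handled means a high detection limit once normalised, so a non-detect need not be a low normalised value. This stands. A reader might infer that the exclusion must have cut off the lower tail, but the documents do not show that, because the five limits are missing.

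It does not follow that the exclusion was neutral. The GSD of 2.62 comes from assigning the group mean to values known only to lie below some limit. If the limits really sit at the geometric mean, the df-corrected censored fit returns 2.85, the plan's own unrounded figure. Over the limits tried, correct handling lowers the GSD hardly at all and can raise it a good deal.

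Other points also have weight:
- Section 6.3 calls ICC 0.3 a likely upper bound and expects a value near zero.
- Section 6.4 asks only that fRA95 be approximately 3. At GSD 3.3 and ICC 0.3 the 95th percentile is still within 3-fold 93.8% of the time.
- The task force already preferred 2.9 to the aerosol-only 2.1. A censored aerosol-only fit with limits at the lowest detect gives about 2.4 to 2.5, still below 2.9.

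These points limit the consequence. They do not support the 3.0 in Table 6 as an unqualified result, since the plan sized the study at ICC 0.3 and justified 2.9 by the pooled data.

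**Conclusion.** The planning GSD was computed by discarding left-censored data, without justification or sensitivity analysis, and the design has almost no room at the ICC used for sizing. Three-fold accuracy for the 95th percentile at ICC 0.3 is therefore not demonstrated. It is missed if the normalised limits are near or below the lowest detects: GSD 3.3 to 3.9 and fRA95 from 3.2 to 4.0, depending on the handling and on which definition of fRA95 is used. It is met if the limits are at or above the group geometric means, where GSD stays at about 2.8.

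A reader might go further and conclude that 18 MEs do not deliver 3-fold accuracy. The documents do not support that. The result depends on five unreported limits, and any miss falls mainly on the 95th percentile at higher ICC. At ICC 0 the benchmark holds for GSD 3.3 to 3.9 (fRA95 2.4 to 2.7). At GSD 3.3 and ICC 0.3 the arithmetic mean still meets it, at about 2.8.

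All of this assumes the plan's lognormal model with a common log SD. Under that model a wider lower tail affects the mean and 95th percentile only through the fitted SD.

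**What to change.** Obtain from the CMA data the detection limits and amounts of active ingredient handled for the five excluded MEs. Re-estimate the common log SD, with separate study means, treating the five as left-censored at their own normalised limits. Restate Table 6 for 3 × 6 MEs over the resulting GSD range, say which definition of fRA95 is used, and give the largest ICC at which 3-fold still holds. If the limits cannot be recovered, show the range of assumed limits and state that the benchmark at ICC 0.3 is conditional on them.

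The cost is a few hours of re-analysis and possibly a less favourable Table 6. No extra subjects are needed to correct the figure. It is best settled before sites are fixed: at GSD 3.32 and ICC 0.3, 6 sites × 3 MEs (still 18) gives fRA95 of 2.7 to 2.8, at the expense of more sites.
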